8.4 Visit 3/Week 1 (Telephone/Email Visit) \pm 2 days

- Interim history review
- Concomitant medication review
- Adverse event review
- Study medication compliance review

8.5 Visit 4/Week 2 (Office Visit) \pm 2 days

- Blood pressure, heart rate, respiratory rate, temperature
- Weight
- Blood work
 - CBC
 - Comprehensive metabolic profile
 - Serum atomoxetine level
 - NET occupancy
 - Norepinephrine metabolites (catecholamines)
- Interim history review
- Concomitant medication review
- Adverse event review
- Suicidality assessment
- Study medication accountability
- Study medication dispensed

8.6 Visit 5/Week 3 (Telephone/Email Visit) \pm 2 days

- Interim history review
- Concomitant medication review
- Adverse event review
- Study medication compliance review

8.7 Visit 6/Week 4 (Office Visit) \pm 2 days

- Blood pressure, heart rate, respiratory rate, temperature
- Weight
- Blood work
 - CBC
 - Comprehensive metabolic profile
 - Serum atomoxetine level
 - NET occupancy
 - Norepinephrine metabolites (catecholamines)

- Interim history review
- Concomitant medication review
- Adverse event review
- Suicidality assessment
- Study medication accountability
- Study medication dispensed

8.8 Visit 7/Week 5 (Telephone/Email Visit) \pm 2 days

- Interim history review
- Concomitant medication review
- Adverse event review
- Study medication compliance review

8.9 Visit 8/Week 6 (Office Visit) \pm 2 days

- Blood pressure, heart rate, respiratory rate, temperature
- Weight
- ECG
- Physical and neurologic exams
- Blood work
 - CBC
 - Comprehensive metabolic profile
 - Serum atomoxetine level
 - NET occupancy
 - Norepinephrine metabolites (catecholamines)
- Interim history review
- Concomitant medication review
- Adverse event review
- Suicidality assessment
- Study medication accountability
- Study medication dispensed

8.10 Visit 9/Week 7 (Telephone/Email Visit) \pm 2 days

- Interim history review
- Concomitant medication review
- Adverse event review
- Study medication compliance review

8.11 Visit 10/Week 11 (Telephone/Email Visit) \pm 2 days

- Interim history review
- Concomitant medication review
- Adverse event review
- Study medication compliance review

8.12 Visit 11/Week 18 (Office Visit) ± 2 days

- Blood pressure, heart rate, respiratory rate, temperature
- Weight
- Physical and neurologic exams
- Blood work
 - CBC
 - Comprehensive metabolic profile
 - Serum atomoxetine level
 - NET occupancy
 - Norepinephrine metabolites (catecholamines)
- Suicidality assessment
- Study medication accountability
- Study medication dispensed

8.13 Visit 12/Week 22 (Telephone/Email Visit) ± 2 days

- Interim history review
- Concomitant medication review
- Adverse event review
- Study medication compliance review

8.14 Visit 13/Week 26 (Telephone/Email Visit) ± 2 days

- Interim history review
- Concomitant medication review
- Adverse event review
- Study medication compliance review

8.15 Visit 14/Week 29 (Office Visit) Crossover Visit- May be performed over multiple days.

- Blood pressure, heart rate, respiratory rate, temperature
- Weight
- Physical and neurologic exams
- Cognitive Testing (full battery)
 - MMSE
 - Logical Memory (LM)
 - Clinical Dementia Rating-Sum of Boxes (CDR-SB) assessments
 - Montreal Cognitive Assessment (MoCA)
 - Category Fluency (Animals)
 - Trails A & B
 - Boston Naming Test (30 item)
 - Auditory Verbal Learning Test
 - Clock drawing
 - Neuropsychiatric Inventory IQ
 - ADAS-Cog 13 (with Delayed Word Recall and Number Cancellation)
 - Activities of Daily Living (FAQ)
 - Geriatric Depression Scale (GDS)

- Blood work
 - CBC
 - Comprehensive metabolic profile
 - Serum atomoxetine level
 - NET occupancy
 - Norepinephrine metabolites (catecholamines)
 - Metabolomics
 - Inflammatory biomarkers
 - Primary Panel for Inflammation, Oxidative, and Titrosative Stress
 - Salivary amylase
 - **Brain MRI**
 - **FDG PET¹**
 - **Lumbar puncture ¹(if LP attempt is unsuccessful, may send to radiology for LP under fluoroscopy. CSF will be assayed for:**
 - Glucose
 - Protein
 - Cell count with differential
 - A β 42, tau, phospho tau
 - Inflammatory Biomarkers
 - NE Metabolites (catecholamines)
 - Interim history review
 - Concomitant medication review
 - Adverse event review
 - Suicidality assessment
 - Study medication accountability
 - Study medication dispensed (crossover)
 - Contact subject on the day after PET scan and LP to inquire about new adverse events.
- ¹Subject to remain on drug until LP and imaging are completed.**

8.16 Visit 15/Week 30 (Telephone/Email Visit) \pm 2 days

- Interim history review
- Concomitant medication review
- Adverse event review
- Study medication compliance review

8.17 Visit 16/Week 31 (Office Visit) \pm 2 days

- Blood pressure, heart rate, respiratory rate, temperature
- Weight
- Blood work
 - CBC
 - Comprehensive metabolic profile
 - Serum atomoxetine level
 - NET occupancy

- Norepinephrine metabolites (catecholamines)
- Interim history review
- Concomitant medication review
- Adverse event review
- Suicidality assessment
- Study medication accountability
- Study medication dispensed

8.18 Visit 17/Week 32 (Telephone/Email Visit) \pm 2 days

- Interim history review
- Concomitant medication review
- Adverse event review
- Study medication compliance review

8.19 Visit 18/Week 33 (Office Visit) \pm 2 days

- Blood pressure, heart rate, respiratory rate, temperature
- Weight
- Blood work
 - CBC
 - Comprehensive metabolic profile
 - Serum atomoxetine level
 - NET occupancy
 - Norepinephrine metabolites (catecholamines)
- Interim history review
- Concomitant medication review
- Adverse event review
- Suicidality assessment
- Study medication accountability
- Study medication dispensed

8.20 Visit 19/Week 34 (Telephone/Email Visit) \pm 2 days

- Concomitant medication review
- Interim history review
- Adverse event review
- Study medication compliance review

8.21 Visit 20/Week 35 (Office Visit) \pm 2 days

- Blood pressure, heart rate, respiratory rate, temperature
- Weight
- ECG
- Physical and neurologic exams
- Blood work
 - CBC

- Comprehensive metabolic profile
- Serum atomoxetine level
- NET occupancy
- Norepinephrine metabolites (catecholamines)
- Interim history review
- Concomitant medication review
- Adverse event review
- Suicidality assessment
- Study medication accountability
- Study medication dispensed

8.22 Visit 21/Week 36 (Telephone/Email Visit) \pm 2 days

- Interim history review
- Concomitant medication review
- Adverse event review
- Study medication compliance review

8.23 Visit 22/Week 40 (Telephone/Email Visit) \pm 2 days

- Interim history review
- Concomitant medication review
- Adverse event review
- Study medication compliance review

8.24 Visit 23 /Week 47 (Office Visit) \pm 2 days

- Blood pressure, heart rate, respiratory rate, temperature
- Weight
- Physical and neurologic exams
- Blood work
 - CBC
 - Comprehensive metabolic profile
 - Serum atomoxetine level
 - NET occupancy
 - Norepinephrine metabolites (catecholamines)
- Interim history review
- Concomitant medication review
- Adverse event review
- Suicidality assessment
- Study medication accountability
- Study medication dispensed

8.25 Visit 24/Week 51 (Telephone/Email Visit) \pm 2 days

- Interim history review

- Concomitant medication review
- Adverse event review
- Study medication compliance review

8.26 Visit 25/Week 55 (Telephone/Email Visit) \pm 2 days

- Interim history review
- Concomitant medication review
- Adverse event review
- Study medication compliance review

8.27 Visit 26/Week 58 End of Study Visit (over 2 days) \pm 2 days

- Blood pressure, heart rate, respiratory rate, temperature
- Weight
- ECG
- Physical and neurologic exams
- Cognitive Testing (full battery)
 - MMSE
 - Logical Memory (LM)
 - Clinical Dementia Rating-Sum of Boxes (CDR-SB) assessments
 - Montreal Cognitive Assessment (MoCA)
 - Category Fluency (Animals)
 - Trails A & B
 - Boston Naming Test (30 item)
 - Auditory Verbal Learning Test
 - Clock drawing
 - Neuropsychiatric Inventory IQ
 - ADAS-Cog 13 (with Delayed Word Recall and Number Cancellation)
 - Activities of Daily Living (FAQ)
- Geriatric Depression Scale (GDS)
- Blood work
 - CBC
 - Comprehensive metabolic profile
 - Serum atomoxetine level
 - NET occupancy
 - Norepinephrine metabolites (catecholamines)
 - Metabolomics
 - Inflammatory Biomarkers
 - Primary Panel for Inflammation, Oxidative, and Nitrosative Stress
- Salivary amylase
- Brain MRI
- FDG PET¹
- Lumbar Puncture¹ (if LP attempt is unsuccessful, may send to radiology for LP under fluoroscopy. CSF will be assayed for:
 - Glucose
 - Protein

- Cell count with differential
- A β 42, tau, phospho tau
- Inflammatory Biomarkers
- NE Metabolites (catecholamines)
- Interim history review
- Concomitant medication review
- Adverse event review
- Suicidality assessment
- Study medication accountability
- Contact subject on the day after LP to inquire about new adverse events.

8.32 Patient Retention

Subjects who are enrolled in the study will be reimbursed for parking and transportation costs at the amount of \$25 for each completed in-office study visit, pro-rated for visits completed. Subjects will also be paid \$100 for each MRI, \$100 for each LP and \$100 for each of the three FDG PET scans completed. If all study visits are completed, subjects will receive a total of \$1300 total.

Reimbursement will be made following visits 2b, 11 and 21. Emory University is required to complete form 1099 for any participant payments over \$600 in a year. To comply with this federal mandate the researchers are required to obtain subject's social security number to complete the form.

9. DATA RECORDING, RETENTION, AND MONITORING

9.1 Electronic Case Report Forms

Electronic Case Report Forms will be completed for each patient who signs Informed Consent. All clinical information requested in this protocol will be recorded on the eCRFs. If an error is made on documents collected (source documents), a single line will be drawn through the error and the correct response will be written adjacent to the error; the change will be initialed, and dated.

9.2 Retention And Availability Of Records

The Investigator will make study data accessible to Regulatory Agency inspectors upon request. A file for each patient will be maintained that includes the signed ICF and the Investigator's copies of all source documentation related to that patient. The Investigator will ensure the reliability and availability of source documents from which the information on the eCRF was derived.

Study documentation will be maintained, including documents created or modified in electronic format, for at least 15 years following the completion of the study. ICFs, and adequate records for the receipt and disposition of all study drugs will be retained for a period of 2 years following the Food and Drug Administration (FDA) or other regulatory

approval date of the drug or until 2 years after the drug investigational program is discontinued, unless a longer period is required by applicable law or regulation.

10. STATISTICAL ANALYSIS PLAN

Statistical analyses will be performed using SAS 9.3. Given our expected sample size of 34 at the end of study, we will have some analytical limitations. Therefore, at the 6- and 12-month time points, we will assess the overall change (improvement/worsening) among the preselected RBM analytes found to be significantly different in preliminary studies of CSF markers. We will then statistically compare the percentage of overall change between the atomoxetine and placebo groups using Pearson's chi-square test or a Fisher Exact test (if necessary). Because IL1-alpha and TECK appear to best predict subsequent cognitive decline, we will compare the levels of these inflammatory markers in each group using a Wilcoxon Rank-Sum test. We will also use Spearman's correlation to determine an association between NE levels and these two biomarkers.

12. ASSAY MEASURES AND ANALYSES

12.1 Lab Manual is available for details pertaining to specific collection, processing, storage and transporting guidelines.

12.2 Genotyping for apolipoprotein E4 allele status will be performed in the Emory Genetics Core facility. Apolipoprotein E4 allele status will not be disclosed to study subjects.

12.3 CSF and Serum Biomarkers. AD biomarkers including A β 42, tau, and phospho-tau levels in the CSF will be assayed at baseline, 6 months, and 12 months following atomoxetine or placebo treatment. These assays will be performed in [name] biomarker laboratory using standardized measurements of CSF AD biomarkers (Innogenetics, Ghent, Belgium) on a Luminex-200 platform. Specialty assays for additional markers such as eotaxin-3, TECK and others have also been established and validated. RBM is a commercial vendor performing the multi-analyte panel as described previously ⁴¹.

12.4 Salivary Amylase. a noradrenergic biomarker, will be assayed in the laboratory of [name], using a Salivary α -Amylase assay kit (Salimetrics, State College, PA). Approximately 1 ml of saliva will be collected at baseline, 6- and 12 months following atomoxetine or placebo treatment. Saliva samples will be stored at -20°C until assay.

12.5 Norepinephrine and metabolites will be assayed in the laboratory of [name], Chief of Neurocardiology at NINDS and one of the leading authorities in the field. The assay will use HPLC with electrochemical detection after batch alumina extraction, a method that was perfected in the lab and routinely used for many years. Analytes to be measured include the catechols norepinephrine (NE), epinephrine, and dopamine, the catecholamine precursor DOPA, the main neuronal metabolite of NE (dihydroxyphenylglycol, DHPG), and the main neuronal metabolite of dopamine, dihydroxyphenylacetic acid (DOPAC).

12.6 Drug levels. Serum atomoxetine levels will be assayed using a highly sensitive liquid chromatography tandem mass spectrometry method⁵⁶ established in the Emory clinical laboratories to monitor compliance and quantify dose-response effects.

12.7 NET Occupancy. In the absence of data from PET studies allowing definitive knowledge of NET occupancy as a function of drug dose, an *ex vivo* assay established in the laboratory of [name], will use serum to estimate NET occupancy. Serum samples will be used to directly measure inhibition of active [³H]-monoamine transport in cells expressing the human serotonin, norepinephrine or dopamine transporters. Uptake measured in drug-free baseline serum is compared to that observed in the subject's samples while on drug and expressed as both % baseline uptake and % occupancy. These assays are sensitive to free drug concentrations representative of extracellular space within the brain where transporter inhibition is hypothesized to be correlated with therapeutic efficacy.

12.8 MRI. Brain MRI scan will be obtained or reviewed at screening to verify eligibility, at baseline, at 6 months and after 12 months of treatment or placebo, using protocols adapted from the ADNI study as described below.

MRI films performed clinically within the past two years will be reviewed by the investigators for eligibility in the study. If a subject does not have clinical MRI films available, the MRI will be performed and reviewed prior to performance of the LP for safety reasons and to ensure that the subject meets eligibility criteria.

The 3T MR acquisition sequences 1) Structural MRI, 2) FLAIR, 3) T2*GRE; 4) arterial spin labeling (ASL), 5) neuromelanin enhancement; and 6) resting state connectivity. MRI measurements of brain structure have been shown to demonstrate brain atrophy (which correlates with neuron loss) in MCI and AD and increasing rates of brain atrophy as subjects become more impaired. Therefore, structural MRI is used as a measure of the rate of disease progression, and possibly as a measure of treatment effect, in AD treatment trials. Structural MRI (MPRAGE//IRSPGR) data will be used both as the rate of change as well as a predictor of future change. Cerebrovascular disease (especially white matter lesions (WMLs)) will be assessed with FLAIR. Recently, iron imaging, especially microbleeds (T2* GRE) has been used in anti-amyloid clinical trials, because of the association of microbleeds with anti-amyloid therapy; this will be measured with T2*GRE. Cerebral blood flow, which closely correlates with cerebral hypometabolism as an early biomarker of AD pathogenesis, will be measured by ASL imaging. A novel protocol developed at Emory by Drs. [name] and [name] to visualize neuromelanin containing neurons will be used to quantify norepinephrine containing neurons in the locus coeruleus. Finally, resting state fMRI will be used to determine functional connectivity changes that have recently been observed in AD.

12.8.1 Clinical Read of MRIs

All MRIs will be reviewed by the investigators and the investigator will determine and document any clinically significant findings.

12.9 FDG PET Scan. -Cerebral metabolic rate for glucose (as measured by fluorodeoxyglucose [FDG] uptake) will be obtained at baseline and at 6 and 12 month timepoints in the study.

In preparation of the FDG PET Scan, subjects will be required to fast for at least four (4) hours prior to the scanning session. Subjects' blood glucose is checked prior to scanning and must be < 180 mg.dL. After the injection of 5 mCi of tracer, subjects are in a quiet, dimly lit room with eyes and ears unoccluded for 30 minutes, after which they are placed in the scanner. Data are acquired as 6 x 5 minute frames.

13. OPEN-LABEL EXTENSION

Participants who complete study Visit 26 will be eligible to receive open-label Atomoxetine at the maximum-tolerated dose received during the double-blind phase of the trial. Atomoxetine will be dispensed immediately following Visit 26, after obtaining subject consent, in the following manner:

- 40 mg p.o. – for 2 weeks, followed by telephone visit to assess AEs
- 80 mg p.o. – for 4 weeks, followed by a telephone visit to assess AEs
- 100 mg p.o. for 6 months at a time(or maximum tolerated dose based on data from double-blind phase of the study)

Subjects who elect to participate in the open-label phase of the study will forego study Visit 27. Participants and investigators will remain blinded about when the subjects received drug versus placebo during the active phase of the study. Atomoxetine administered during the open-label phase will be identical in appearance to drug received during the double-blind phase of the trial. Participants who wish to receive open-label drug will be asked to sign a new consent form (after the investigator or study coordinator has explained procedures for the open-label phase of the trial and after all participant questions have been addressed).

Participants who elect to receive open-label drug will be required come to the clinic to have safety labs performed every six months, including CBC with differential and chemistry (including liver enzymes). Once the results of safety laboratory studies are received, open-label Atomoxetine in sufficient quantity for 6 months therapy (100 mg/day) will be dispensed at no cost to the participant. For the duration of open-label participation, participants will undergo an annual MRI and PET scan, in addition to CSF collection via lumbar puncture. In addition, a short battery of cognitive tests (MMSE, CDR) will be performed annually. Participants will be asked to report any adverse events that develop during the open-label phase of the trial.

The open-label phase of the study will be terminated after 2 years (i.e., 104 weeks) following successful completion of the active phase of the study. The P.I. reserves the right to stop open-label dispensing at any time.

14. TABLE 1 Schedule of Assessments

Schedule of Assessments																													
Visit Number	1a	1b	2a	2b	3	4	5	6	7	8	9	10	11	12	13	14	15	16	17	18	19	20	21	22	23	24	25	26	27
Study Week	Screening		Baseline		1	2	3	4	5	6	7	11	18	22	26	29 ¹	30	31	32	33	34	35	36	40	47	51	55	58	62
	a	b ¹	a ¹	b																									
Dosing (max tolerated dose)				10 mg	18 mg	40 mg	60 mg	80 mg	100 mg							10 mg	18 mg	40 mg	60 mg	80 mg	100 mg								
Consent	x																												
Confirm eligibility	x			x																									
Medical history and medication review	x																												
Physical and neurological examination	x			x						x			x			x									x			x	x
Vital signs + height (screening only) & weight	x			x		x		x		x			x			x		x		x					x			x	x
ECG	x									x																		x	x
Blood and/or urine ⁷ for clinical labs	x					x		x		x			x			x		x		x					x			x	x
Serum pregnancy if indicated				x																									
APOE Genotyping				x																									
Blood for biomarkers, drug levels, NE and metabolites		x		x ⁶		x		x		x			x			x		x		x					x			x	x
Labs for future research				x																									
Salivary amylase		x														x													x
MRI		x ³		x ^{4,5}												x													x ⁵
FDG PET				x												x													x
Lumbar puncture		x														x													x ⁵
Study Drug dispensed				x		x		x		x			x ²			x		x		x					x				
Modified Rosen Hachinski	x																												
Telephone Call/Email Contact					x		x		x		x	x		x	x		x		x		x		x	x		x	x		
Cognitive Assessment	x			x												x													x
Suicidality Assessment	x			x		x		x		x			x			x		x		x					x			x	x
Assessment of current medications, interim history, & adverse event review	x			x	x	x	x	x	x	x	x	x	x	x	x	x	x	x	x	x	x	x	x	x	x	x	x	x	x
Study Drug Compliance					x	x	x	x	x	x	x	x	x	x	x	x	x	x	x	x	x	x	x	x	x	x	x	x	
Randomization/Study Arm Crossover				x												x													

¹Visit may be performed over 2 days, ²3 months of study meds dispensed at V11, V23., ³ MRI to be done if no clinical MRI w/ past 2 years for review. ⁴If pre-enrollment MRI is not available at the time of screening, the baseline MRI will be completed prior to screening LP to determine eligibility. ⁵MRI will be done prior to LP to avoid meningeal reactions for subjects who have not had MRI in past 2 years. Early termination will lead to same visit type as termination week 58 visit. ⁶ No NE and metabolites at this visit. ⁷ Urine at Visit 1a only. Areas highlighted in yellow represent office visits. Visit14/Week 29, highlighted in blue is the crossover visit.

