2. SPECIFIC AIMS

2.1 Aim #1 To evaluate safety and tolerability of atomoxetine in individuals with MCI and define the dose-response effect on biomarkers of noradrenergic function.

Although atomoxetine is used clinically for ADHD, it is unknown whether atomoxetine administration will measurably impact indices of NE tone in subjects with MCI and be safe and tolerable in these patients. Safety will be assessed by standard adverse event scales, suicidal ideation monitoring, electrocardiograms, and vital signs. We will determine the maximum tolerated doses of atomoxetine (10, 18, 40, 60, 80, 100 mg po daily) and the dose-response effect on NET inhibition. NE metabolites, serum atomoxetine levels, and NET occupancy will be measured in the blood each week after escalating doses of atomoxetine, and in the CSF after stable maximal tolerated doses.

EXPECTED OUTCOMES: Atomoxetine will be safe, well-tolerated with a treatment-associated drop out rate < 15%, and will show a dose-response effect on blood and CSF markers of noradrenergic tone, including NE and its primary neuronal metabolite dihydroxyphenylglycol (DHPG).

2.2 Aim #2 To assess the effect of chronic atomoxetine treatment (6 months) on biomarkers of inflammation and neurodegeneration in subjects with amnesic MCI.

In rodent models of AD, LC lesions accelerate AD related pathophysiology via dysregulation of microglial function and inflammation, whereas NET inhibition improves microglial function, ameliorates A β plaque deposition, and increases spatial and social memory. The effect of NET inhibition on inflammation and AD biomarkers in a clinical population is unknown. This study will examine the effect of atomoxetine on:

Biomarkers of inflammation (including TNF-alpha, IL1, IL-6, IL-17, IL-10, IL-4 and BDNF and VEGF) in blood and CSF using the Rules Based Medicine (RBM) InflammationMAP analyte panel. We predict that atomoxetine treatment will measurably reduce CSF levels of pro-inflammatory biomarkers and increase levels of anti-inflammatory biomarkers.

CSF biomarkers of AD (A β 40, A β 42, tau, phospho-tau) using highly sensitive and standard methods adopted in ADNI. Because these markers are most dynamic during preclinical stages of AD pathogenesis, we predict that 6 months of atomoxetine treatment will not result in any significant change in CSF A β , tau and phospho-tau levels compared to placebo.

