4.3 Atomoxetine Dosing. Atomoxetine is a selective norepinephrine reuptake inhibitor that is approved by the FDA at a dose range of 10-100 mg daily for the treatment of ADHD in adults. It has well-established efficacy and safety in the treatment of ADHD. The drug is available for purchase (manufacturer Eli Lilly). Our rationale for atomoxetine dosing is based on prior studies.

The trial will consist of a double-blind administration of either atomoxetine, with dose escalation from 10-100 mg po daily, or placebo. The schedule will be 10 mg po once daily (after breakfast to prevent nausea), with weekly increases pending tolerability: 18 mg week 2, 40 mg week 3, 60 mg week 4, 80 mg week 5, and then 100 mg week 6 unless side effects emerge. If there are any concerns about side effects, the dose will be decreased to the previously tolerated level. Clinician judgment will be used to maintain dose or after one

week increase by 10 mg. Dosage will be increased in the same manner for subjects who crossover from placebo to atomoxetine at the six month timepoint.

A compounding pharmacy approved by Emory's Investigational Drug Service (IDS) will form capsules containing atomoxetine or matching placebo. Study medications will be stored at the Emory IDS and dispensed by study personnel. Subjects will be dispensed the initial 10 mg or placebo capsules after the baseline visit (2b), and will return every 2 weeks for safety assessment and additional medication dispensing. Crossover to either placebo or active treatment will occur at week 29. Participants will be provided sufficient medication for dosing adjustments. Weekly phone visits during this dose escalation phase will provide additional review of safety and tolerability. Dosing instructions will be provided at each phone call or visit.

4.4 Future research samples. Per individual subject consent, blood, cell lines and cerebrospinal fluid samples will be stored indefinitely and may be used for future investigation regarding atomoxetine pharmacology and/or side effects, potential development of new biomarkers, and potential treatments for Alzheimer's disease. Samples may also be used to deal with future safety issues for atomoxetine or related drugs for Mild Cognitive Impairment or Alzheimer's disease that are not known at the present time. These stored samples may also be used for genetic (DNA) research.

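### Section 13 offers the double-blind maximum tolerated dose in the open-label extension, but its 40 mg and 80 mg steps and its supply sentence carry no such cap

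*Combined protocol and SAP*

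**What the plan says.** Section 13 opens by making participants who complete Visit 26 "eligible to receive open-label Atomoxetine at the maximum-tolerated dose received during the double-blind phase of the trial". It then lists how the drug is dispensed:

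- 40 mg "for 2 weeks, followed by telephone visit to assess AEs";
- 80 mg "for 4 weeks, followed by a telephone visit to assess AEs";
- 100 mg for six months at a time, with the parenthesis "or maximum tolerated dose based on data from double-blind phase of the study".

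A later sentence in the same section describes six-monthly resupply at 100 mg/day, without that parenthesis.

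The blind continues: "Participants and investigators will remain blinded about when the subjects received drug versus placebo during the active phase of the study".

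Elsewhere the protocol expects some participants to stop below the top dose. Section 2.1 states: "We will determine the maximum tolerated doses of atomoxetine (10, 18, 40, 60, 80, 100 mg po daily"). Section 4.3 states: "If there are any concerns about side effects, the dose will be decreased to the previously tolerated level". It then lets the clinician hold that dose or, after a week, raise it by 10 mg. Section 6.1 lowers the dose when systolic pressure reaches 160 or diastolic pressure reaches 100. In Table 1 (section 14), the row labelled "Dosing (max tolerated dose") runs the 10 to 100 mg steps in both crossover periods.

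**The concern.** The opening sentence sets the dose by what the participant tolerated. The list sets it by a fixed schedule and returns to tolerance only at the last step. Writing the cap on one step of three invites staff to treat the other two as fixed, and the list has no step below 40 mg. A participant whose dose was held or lowered in the blinded phase could then be dispensed more than a dose already recorded as the limit.

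Participant safety is at stake. The extension begins after Visit 26, so the 6- and 12-month comparisons, the sample size and the power are not involved.

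A second gap follows from the crossover. Each participant has a highest maintained dose in each period, one of them on placebo. Section 13 does not say how blinded staff are to know which one is the atomoxetine limit.

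**Working it through.** The plan gives no figure to reproduce here. The check compares the fixed steps with the limits that the protocol allows.

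**Inputs**
- Fixed steps: 40 mg for 2 weeks, then 80 mg for 4 weeks (section 13).
- Listed dose levels: 10, 18, 40, 60, 80 and 100 mg (section 2.1).
- Intermediate limits are possible because section 4.3 allows 10 mg increases after a step-down, for example 40 + 10 = 50 mg and 60 + 10 = 70 mg. The six listed levels are therefore not the full set.

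**Formula.** For a maintained atomoxetine limit L, the excess at a fixed step D is max(0, D − L).

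| Limit L (mg) | Excess at 40 mg, 2 weeks | Excess at 80 mg, 4 weeks | Weeks above limit |
|---|---|---|---|
| 10 | 40 − 10 = 30 | 80 − 10 = 70 | 2 + 4 = 6 |
| 18 | 40 − 18 = 22 | 80 − 18 = 62 | 2 + 4 = 6 |
| 40 | 0 | 80 − 40 = 40 | 4 |
| 50 | 0 | 80 − 50 = 30 | 4 |
| 60 | 0 | 80 − 60 = 20 | 4 |
| 70 | 0 | 80 − 70 = 10 | 4 |
| 80 or more | 0 | 0 | 0 |

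These figures assume that the list is followed literally and that nobody steps the dose down. The third step is capped by its own parenthesis. The supply sentence conflicts with that parenthesis for any limit below 100 mg, but may describe only the quantity dispensed.

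**What is scheduled during the two steps.** Each telephone contact follows its step, so the scheduled calls fall at about 2 and 6 weeks. Section 13 schedules no blood-pressure reading in that time; its six-monthly clinic requirement is blood tests. By contrast, blinded escalation has office visits with vital signs at Weeks 2, 4 and 6 (sections 8.5, 8.7 and 8.9). Visit 26 includes vital signs and an ECG, but participants who took atomoxetine first have been on placebo since Week 29, so those readings do not show how they tolerate atomoxetine.

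**Identifying the limit.** Suppose 60 mg was maintained on atomoxetine and 100 mg on placebo. Taking the higher gives 100 mg, which is 40 mg above the atomoxetine limit; taking the lower gives 60 mg. With the doses reversed (100 mg on atomoxetine, 60 mg on placebo), the lower is 40 mg below what was tolerated on drug. The lower of the two can never exceed the atomoxetine dose, but it can fall short of it.

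**How many people.** The documents do not say. Section 1.4 reports a mean tolerated dose of 89.6 mg in 12 patients with Parkinson's disease, and 5 withdrawals for adverse effects among 47 patients with mild to moderate Alzheimer's disease at up to 80 mg. Neither gives the share of people with MCI who would finish this trial on less than 80 mg.

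**The case against.** The strongest reply is that the opening sentence already governs and the list only describes how to climb to the tolerated dose. The drafting elsewhere supports this. Section 4.1 attaches the tolerated-dose clause only to the 100 mg maximum, and Table 1 puts one tolerated-dose label over a row of uncapped values. On that view, harm needs staff to ignore the opening sentence and the step-down rule and, for the six-week cases, to let the first telephone contact change nothing. Entrants must also have completed both periods and signed a new consent. Doses stay within the 10 to 100 mg range, and the investigator may stop dispensing at any time.

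Most of this stands. A reader might infer that section 13 flatly contradicts itself or orders dosing above tolerance; the documents do not support that, because the general-cap reading is available. Nor is every dose above an earlier level forbidden, since section 4.3 permits cautious re-challenge. But its increment is 10 mg after a week, so it does not cover giving 80 mg to someone held at 60 mg. The step-down rule and the right to stop dispensing respond to a problem; they do not prevent dispensing above a known limit.

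A reader might also infer that the tolerated dose has no definition at all. That goes too far. Sections 2.1 and 6.1 tie it to atomoxetine, and under section 7.5 the biostatistician and the Investigational Drug Service hold the randomisation scheme. What is missing is the route by which blinded staff obtain the right figure.

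**Conclusion.** The inconsistency is real, and its consequences are limited. Followed literally, the list doses anyone limited below 80 mg above that limit for 4 weeks, and anyone limited below 40 mg for 6 weeks, by the amounts in the table. This assumes that the opening sentence is not applied as a general cap and that no step-down occurs. The number affected is unknown and probably small.

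A reader might take the six-week figures as the expected exposure. They are the worst case, for the lowest limits only. A reader might also suspect an effect on the trial's results; there is none, because the extension follows the last blinded assessment. This is a minor safety correction, worth making because a dosing instruction should not rely on staff inferring a cap that is written on only one step of three.

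**What to change.** Add *or the double-blind maximum tolerated dose of atomoxetine, whichever is lower* to the 40 mg step, the 80 mg step and the 100 mg/day supply sentence.

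Then state how that dose is identified while investigators remain blinded to period. Either of two routes would do:

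- Use the lower of the doses maintained in the two periods, after any step-down. This needs no disclosure, but someone whose dose was limited while on placebo may be under-dosed.
- Have the Investigational Drug Service supply the atomoxetine-period dose. This gives the right figure, but may hint at which period was active.

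The choice belongs to the sponsor. Restating the section 6.1 blood-pressure rule is not proposed: it is not confined to the blinded phase, and would add little while no reading is scheduled during these steps.

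The cost is a few words in three places and one definition. No visit is added and neither route needs a general code-break.
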